3.3 Exploratory Objectives

The exploratory objectives are:

1. To compare rates of hemoglobin reductions of ≥ 2 g/L from pre-procedure to 24-48 hours post procedure in the Edoxaban and Warfarin groups
2. To compare change in hemoglobin from pre-procedure to 24-48 hours post procedure in the Edoxaban and Warfarin groups
3. To compare the rates of other events of interest, including
 - Hemoglobin decrease of 1.5Gm% or greater after 24 to 48 hrs
 - Other cardiac procedures
 - Hematoma requiring no intervention
 - Device Infection
 - Device explanation
 - Major intracranial hemorrhage
 - Vascular events
 - Myocardial Infarction (MI)
 - Cardiovascular Hospitalization
 - Hospitalization after procedure discharge and prior to study conclusion
 - Stroke and death composite

4. Study Design

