DURATION OF PATIENT PARTICIPATION AND DURATION OF STUDY	
Screening: 7-26 days
 
Treatment: 5 days of randomized therapy prior to procedure (which is a single day)
 
Follow-up: 180 days

CONCOMITANT MEDICATIONS	Allowed as per approved FDA guidelines
EFFICACY EVALUATIONS	
PRIMARY ENDPOINT	Major local or systemic bleeding as defined in the protocol at 30 days after implant procedure
SECONDARY ENDPOINTS	The secondary objectives are to compare the rates of thrombotic events (embolism or stroke) through 6 months following the procedure in the Edoxaban and Warfarin groups and the rates of MACE events through 6 months following the procedure in the Edoxaban and Warfarin groups
OTHER EVALUATIONS	The exploratory objectives are to compare rates of hemoglobin reductions from pre-procedure to 24-48 hours post procedure in the Edoxaban and Warfarin groups
SAFETY EVALUATIONS	Safety monitoring during the study will be performed by an independent data monitoring committee (DMC), as well as medical and clinical monitors

	and the coordinating center. Sites will be monitored by a clinical monitor at least once during this short trial. Clinical sites will be required to report all procedure related complications, deaths and major adverse events to the medical monitor within 24 hours of learning of the event. All events will be adjudicated by an independent events committee.
PLANNED INTERIM ANALYSES	When approximately 200 subjects have completed the study through the 30-day visit, an interim analysis for safety will be conducted by an independent data monitoring committee. Serious adverse events will be monitored by the committee on an ongoing basis throughout the study. Based on the primary outcome in these 200 subjects, the study may continue to enroll up to 200 additional subjects, or be terminated.
STATISTICS Primary Analysis Plan	This study contains an internal pilot, and the primary endpoint will be evaluated when 200 patients have reached 30-days post procedure or withdrawn. Based on the primary outcome in these 200 patients, the study may enroll up to 200 additional subjects, or be terminated. Bleeding rates will be compared for non-inferiority using a 1-sided exact test (Primary Endpoint). If non-inferiority of Edoxaban is demonstrated, superiority will be assessed using a 2-sided exact test (Secondary Endpoint).

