4.2 Justification of key elements of study design

4.2.1 Primary Endpoint

Peri-procedural bleeding and major local bleeding is of clinical concern for patients who require anticoagulation. Though catastrophic bleeding is rare, bleeding requiring clinical intervention is more frequent and can be studied in a modestly sized trial. Unlike strict use of change in hemoglobin, the need for intervention with vitamin K or blood products is recognizable to patients. Reduction in the need to administer an intervention for a procedural bleed should also result in lower health care resource utilization and costs.

Major local or systemic bleeding is defined as one of the following events:

- Significant hematoma requiring further surgery, resulting in prolongation of hospitalization, or requiring interruption of oral anticoagulation therapy
- Blood transfusion (permitted if hemoglobin is below 8 gm%, or 9 gm% in patients with active myocardial ischemia e.g. acute coronary syndrome)
- Surgical or interventional procedure to control bleeding that is symptomatic (shock, severe hypotension (90 mm hg systolic) or angina or myocardial infarction, which is not amenable to conservative measures (pressure dressing, ice packs) or volume expansion with intravenous fluids)
- Use of reversal agent injection to control bleeding leading to clinically manifest shock (e.g. hypotension requiring pressors, oliguria etc.) or death, severe and symptomatic hypotension (90 mm hg systolic or lower) or angina or hemoglobin decline to below 8 gm% not amenable to conservative measures (pressure dressing, ice packs or volume expansion with intravenous fluids)
- Hemorrhage leading to stroke or eventual fatality

(INR- guidelines for vitamin K injection or blood products will be established- see guideline below).

(aPTT or anti- factor Xa assay may or may not be available for Edoxaban to guide reversal – clinical and Hemoglobin guidelines as established above will be employed to guide use of reversal with blood products or transfusion).

Recommendations for Managing Elevated INRs or Bleeding in Patients Receiving VKAs

Condition	Suggested Intervention
INR less than 4.5 but above	Hold or reduce Warfarin dose. Resume Warfarin when INR is therapeutic.

therapeutic	

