10.4 Analysis of secondary objectives

The assessment of superiority of Edoxaban will be assessed if the primary endpoint analysis shows non-inferiority. In this case, the test will use the same methodology but will test the hypothesis that the difference in bleed rates (Warfarin – Edoxaban) is significantly different from zero rather than significantly greater than -1.5%.

With the exception of continuous change in hemoglobin, all remaining secondary endpoints are binary. They will be summarized with the number and percent in each group, and as rates based on the total patient-years of follow-up. The treatments will be compared as for the primary endpoint. If there are sufficient numbers of events, survival analysis techniques will also be used.

Continuous change in hemoglobin will be compared using ANCOVA, adjusted for baseline and trial stratification factors.

A statistical analysis plan (SAP) containing more information about end of study statistical analyses will be finalized prior to database lock.

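### Exploratory objective 1 counts hemoglobin falls of at least 2 g/L (0.2 gm%), while all four other hemoglobin thresholds are in gm%; the unit and threshold need confirming

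*Combined protocol and SAP*

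**What the plan says.** Section 3.3 (Exploratory Objectives) has three numbered objectives that use hemoglobin:

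- Objective 1 compares the arms on rates of "hemoglobin reductions of ≥ 2 g/L from pre-procedure to 24-48 hours post procedure".
- Objective 2 compares the continuous change between the same two time points.
- Objective 3 lists other events of interest, the first being "Hemoglobin decrease of 1.5Gm% or greater after 24 to 48 hrs".

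Section 4.2.1 (Primary Endpoint) uses hemoglobin in two components of major bleeding. The transfusion component reads "Blood transfusion (permitted if hemoglobin is below 8 gm%, or 9 gm% in patients with active myocardial ischemia". The reversal-agent component includes "hemoglobin decline to below 8 gm% not amenable to conservative measures".

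The synopsis, under Other Evaluations, gives the exploratory aim as "to compare rates of hemoglobin reductions from pre-procedure to 24-48 hours post procedure", with no threshold and no unit. Section 10.4 says "Continuous change in hemoglobin will be compared using ANCOVA, adjusted for baseline and trial stratification factors". It also says that the remaining binary endpoints are compared in the same way as the primary endpoint, but it gives no hemoglobin cut.

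**The concern.** Objective 1 is the only place where hemoglobin is expressed in g/L. Read literally, it counts a fall of 0.2 gm% as an event, while two items later the same section counts a fall of 1.5 gm%. Every patient who meets the second then meets the first, and the first-listed hemoglobin objective is much the looser of the two.

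Whoever programs the endpoint must either apply 0.2 gm% or guess that 2 gm% was intended. The two readings differ tenfold and would give very different event rates. Programmed as written, the endpoint would count very small changes, many of them ordinary variation between two blood draws, in a trial whose purpose is to compare bleeding. The trial is also open label, so settling the unit after data have been seen would amount to choosing the endpoint post hoc.

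**Working it through.** The threshold is a definition, so there is no derived figure in the plan to reproduce. The check is a unit conversion, a count of thresholds, and an illustration of the effect.

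**Conversion.** 1 gm% = 1 g/dL = 10 g/L.

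- Objective 1 as written: 2 g/L ÷ 10 = 0.2 gm%.
- Objective 3, first item: 1.5 gm% × 10 = 15 g/L.
- Ratio of the two cuts: 15 ÷ 2 = 7.5.
- If objective 1 was meant in gm%: 2 gm% = 20 g/L, and 20 ÷ 2 = 10 times the written value.

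**Count of the other hemoglobin thresholds.**

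| Where | Threshold | Unit |
|---|---|---|
| 3.3, objective 3 | fall of 1.5 | gm% |
| 4.2.1, transfusion | below 8 | gm% |
| 4.2.1, transfusion with active ischemia | 9 | gm% |
| 4.2.1, reversal agent | below 8 | gm% |

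All four are in gm%.

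**Nesting.** As written, the 1.5 gm% events are a subset of the objective 1 events (0.2 < 1.5). If 2 gm% was meant, the objective 1 events are a subset of the 1.5 gm% events (2 > 1.5). The order reverses with the unit.

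**Illustration.** The documents give neither a mean fall nor an SD. Assume that the fall is normal with mean μ and SD σ between 0.5 and 1.2 gm%. The share meeting a cut c is 1 − Φ((c − μ)/σ). For example, with μ = 0 and c = 0.2: σ = 0.5 gives 1 − Φ(0.40) = 0.345, and σ = 1.2 gives 1 − Φ(0.167) = 0.434.

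| Mean fall (gm%) | Fall ≥ 0.2 (as written) | Fall ≥ 1.5 | Fall ≥ 2.0 |
|---|---|---|---|
| 0 | 34-43% | 0-11% | 0-5% |
| 0.2 | 50% | 0-14% | 0-7% |
| 0.5 | 60-73% | 2-20% | 0-11% |
| 1.0 | 75-95% | 16-34% | 2-20% |

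Among patients counted as written, the share whose fall is below the protocol's own 1.5 gm% cut is [P(≥0.2) − P(≥1.5)] / P(≥0.2). With μ = 0 and σ = 1.2 this is (0.434 − 0.106)/0.434 = 0.756. Over the assumed SD range it is 76-100% at mean fall 0, 66-97% at 0.5 and 55-83% at 1.0.

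**The case against.** The strongest reply is that nothing in the text is contradictory. A fall of 2 g/L and a fall of 1.5 gm% can stand together as nested cuts, mixed units alone do not prove an error, and no 2 gm% threshold appears anywhere in the documents. That is correct, and it is why the point is to confirm the definition rather than to assert an error.

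A second reply is that little depends on it. The objective is exploratory, and section 4.2.1 deliberately bases the primary endpoint on interventions rather than on change in hemoglobin alone. The continuous comparison and the 1.5 gm% event keep the information on blood loss, and with both values collected any cut can be applied later. This limits the severity. It does not remove the need to fix a stated between-arm comparison before data are seen.

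Third, the percentages rest on assumptions. With SD 0.3 to 1.0 gm% and no mean fall, for instance, the share meeting the written cut is 25-42% instead of 34-43%. The sevenfold and tenfold ratios need no such assumption.

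Two smaller caveats also stand. The 1.5 gm% item names the 24 to 48 hour timing but no baseline, so a pre-procedure baseline is a reasonable inference and not text. Section 10.4 discusses continuous change in hemoglobin under secondary endpoints although section 3.3 calls it exploratory, so its tier is not entirely clear.

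**Conclusion.** The concern holds. Objective 1 as written is a fall of 0.2 gm%, which is 7.5 times looser than the other hemoglobin fall in the same list. It is expressed in a unit used nowhere else, and no other section resolves it. These facts come directly from the documents. That 2 gm% was intended is likely, but it is an inference. The event-rate ranges depend on the assumed normal distribution, SD and mean fall, and serve only to show that the two readings would produce very different endpoints.

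The effect is confined to this one exploratory endpoint. The primary endpoint, the sample size, the secondary objectives in section 3.2, the 1.5 gm% event and the ANCOVA of continuous change do not use the cut. It should be corrected, but it does not threaten the trial's main conclusion.

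**What to change.** Before any outcome data are reviewed, the sponsor should:

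1. Confirm the intended threshold and unit for objective 1 and correct section 3.3 accordingly. The change to at least 2 g/dL (2 gm%, 20 g/L) should be made only if that was meant. If 2 g/L is deliberate, say so and give the reason.
2. Reconcile objective 1 with the 1.5 gm% item: state the baseline for both, and state which event is nested in which.
3. Give the threshold in the synopsis and use one hemoglobin unit throughout the protocol and SAP.

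The cost is a one-line correction in section 3.3 and in the synopsis, carried into the SAP, which section 10.4 says is to be finalized before database lock. No added data are needed, because section 7 and Appendix A already schedule hemoglobin before the procedure and at 24-48 hours.

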4.1 Overview

This study is a randomized, open label, active-controlled trial with a safety extension (follow-up phase). It is designed to compare bleeding, local or systemic, within 30 days of cardiac rhythm device implant (acute phase) for non-valvular AF among patients randomized to continuous Warfarin or interrupted

Edoxaban. Randomization will be stratified by device type and HAS-BLED score (≤ 2 or ≥ 3). Patients will be randomized in a 1:1 ratio to receive interrupted Edoxaban or continuous Warfarin. This study contains an internal pilot opportunity to adjust the sample size or terminate the study, and there will be an interim analysis of the primary endpoint when 200 patients have reached 30-days post procedure or withdrawn. Based on the primary outcome in these 200 patients, the study may:

[figure not shown]
- Enroll 200 additional patients (pacemaker capped at 100 patients, ICD capped at 150 patients)
- Enroll 100 additional patients
- Be terminated

The study design is outlined in Figure 1.

Figure 1:

Study Design Flow Chart

Study Timeline

- Seamless design, enrollment does not stop between phases
-  Opportunity to stop if Part I objectives are not met
- Minimal resource commitment to Part II if Part I objectives not met
- For Part II, all sites enrolling, experience should lead to improved data quality compared to Part I
- Phases analyzed separately (primary) and combined

Eligible subjects must be stable on a therapeutic dose of Warfarin (INR 2-3) for three weeks prior to randomization. If potential patients are taking an anticoagulant besides Warfarin, or otherwise not meeting this criteria, must be switched to Warfarin and complete 3 weeks of dosing with INRs in the therapeutic range (run-in period) at randomization.

Comment [s1]: Segment into two sentences.
Insert period

Comment [s2]: delete

Comment [s3]: delete

Comment [s4]: Insert

The final INR should be performed on the day of randomization, and the procedure should be scheduled a minimum of 5 days and at most 15 days after randomization. Once eligibility has been confirmed and informed consent has been obtained, patients will be randomized via an interactive secure web randomization system. Patients will be randomized in a 1:1 ratio to Edoxaban or Warfarin. Randomization will be blocked by HAS-BLED score, and based on a randomization list, which will be created prior to commencement of the study.

At randomization, subjects will be provided with a drug kit containing either open-label Edoxaban or Warfarin for 30 days at a randomization visit. Patients randomized to Warfarin will take Warfarin on the day of procedure and patients randomized to Edoxaban will receive no drug on the day of the procedure.

Routine clinical care will be implemented with patients being scheduled for discharge within 24 hours of admission to maintain ambulatory procedural status. Patients requiring longer lengths of stay will have documentation of conditions warranting such care.

The routine standard of care (SOC) is instituted after the procedure, with a pre-discharge visit (4 to 24 hours after procedure), wound care visit (usually 1 to 2 weeks after the procedure) and standard device clinical follow-up procedures. These can include one month, three month or six month visits or remote monitoring as clinically employed in the study.

In the event of an acute procedural bleed, blood products or vitamin K may be administered. In this case, the patient will be counted as having met the primary endpoint. The primary outcome of major bleed will be assessed at the 30-day visit. The medical monitor will confirm that the primary endpoint has been assessed.

After the 30-day assessment, patients will continue to take the randomized anticoagulant unless it becomes medically necessary to change it. The MACE components will be collected at the time of the 6-month in-clinic visit.

There will be a telephone follow-up at 3 months after the CIED procedure for MACE and hospitalizations and vital status. There will be a face to face visit at 6 months which will result in study follow up completion and final patient assessment for safety endpoints, hospitalizations and vital status.

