INR 4.5 to 10 with no evidence of bleeding	
Hold Warfarin. Resume Warfarin when INR is therapeutic.
 
Vitamin K not routinely recommended if no evidence of bleeding.
 
Vitamin K can be used if urgent surgery needed (less than 5 mg, with additional 1 to 2 mg in 24 hrs. if needed) or bleeding risk is high (1 to 2.5 mg).

INR greater than 10 with no evidence of bleeding	
Hold Warfarin therapy and administer vitamin K 2.5 mg to 5 mg orally.
 
Monitor INR.
 
Resume Warfarin at lower dose when INR therapeutic.

Serious bleeding at any elevation of INR or Life-threatening bleeding	
Consult Hematology.
 
Hold Warfarin.
 
Administer intravenous vitamin K 5 mg to 10 mg by slow infusion or administer blood products as appropriate.

*In patients with mild to moderately elevated INRs without major bleeding, give vitamin K or blood products as appropriate. Adapted from ACCP Evidence-Based Clinical Practice Guideline *Chest* 2012; 141(Suppl 2): e154S-88s.

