4.2.3 Timing of primary endpoint evaluation

Other studies in cardiovascular medicine such as those for interventions during acute myocardial infarction or chronic ischemic heart disease consider bleeding events through 30-days post-procedure, and so it is a commonly used clinical timeframe. Because this trial is examining a surgical intervention, there is potential for bleeds and other acute complications. If this happens, the open label design allows investigators to make appropriate treatment decisions as quickly as possible. As always, open-label designs have an increased risk of bias. To combat this risk, we have defined a primary endpoint with minimal patientivity (see section 4.2.1). We will also have a blinded adjudication committee review each potential primary endpoint event to confirm that the study definition has been met.

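### Section 4.1 counts any acute procedural bleed given vitamin K or blood products as a primary event; the Section 4.2.1 definition does not, and a result resting on few events is sensitive to the difference

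*Combined protocol and SAP*

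**What the plan says.** Three places in the combined protocol and SAP bear on what counts as a primary event.

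- **Section 4.1 (Overview)**, on acute bleeding at the procedure, states: "blood products or vitamin K may be administered. In this case, the patient will be counted as having met the primary endpoint". No severity condition is attached.
- **Section 4.2.1 (Primary Endpoint)** gives a list: "Major local or systemic bleeding is defined as one of the following events". Vitamin K as such is not on it. The nearest item is "Use of reversal agent injection to control bleeding leading to clinically manifest shock", which continues with death, severe symptomatic hypotension, angina, or hemoglobin below 8 gm% despite conservative measures. Blood transfusion is a separate item. So is a significant hematoma that leads to further surgery, a prolonged stay or interruption of anticoagulation.
- **Section 4.2.3** answers the risk of open-label bias by saying "we have defined a primary endpoint with minimal patientivity (see section 4.2.1", and then has a "blinded adjudication committee review each potential primary endpoint event to confirm that the study definition has been met".

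The rationale in 4.2.1 is looser than its own list. It says that "the need for intervention with vitamin K or blood products is recognizable to patients", again without a severity condition. The synopsis refers only to the definition in the protocol, which does not settle the matter.

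**The concern.** The same patient can be a primary event under 4.1 and a non-event under 4.2.1. The clearest case is a non-severe bleed treated with vitamin K that meets no other listed criterion. The footnote to the vitamin K table in 4.2.1 foresees vitamin K or blood products without major bleeding, so such patients are plausible.

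Three features make the wording matter:

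- Few events are expected, so one or two reclassified patients can move the result.
- Treatment is open label, so the team that decides on vitamin K knows the arm. The vitamin K guidance covers only patients on vitamin K antagonists. Events counted under 4.1 alone may therefore fall mainly on Warfarin, which would favor non-inferiority of Edoxaban.
- The primary outcome in the first 200 patients decides whether the trial stops or enrolls 100 or 200 more. A counting rule settled after that look could appear to be driven by the data.

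**Working it through.** **Inputs.** One-sided type I error 0.025 and margin 1.5 points (Section 10); 30-day rates 3.51% Warfarin and 0.5% Edoxaban, 300 patients for about 80% power (Section 10.2); 1:1 allocation (Section 4.1); maximum 400 patients (synopsis). Section 10.3 names only an exact test.

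**Assumptions.** The test is an exact unconditional test ordered by the Farrington-Manning score. The 3.51% is taken as the Warfarin rate under 4.2.1. The documents do not say this, but Section 10.1 takes the rate from a trial that Section 1 describes as reporting clinically significant pocket hematomas, which resembles the first 4.2.1 item.

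**Step 1: reproduce the stated power.** Distance to the margin: 0.0351 − 0.005 + 0.015 = 0.0451. SE = √[(0.0351×0.9649 + 0.005×0.995)/150] = 0.01609. Then 0.0451/0.01609 = 2.803, and Φ(2.803 − 1.960) = 80.0%. The exact test gives 79.6%. Both match the plan.

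**Step 2: expected events at 150 per arm.** Warfarin 150 × 0.0351 = 5.3; Edoxaban 150 × 0.005 = 0.75.

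**Step 3: smallest Warfarin count that gives non-inferiority.**

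| Edoxaban events | 0 | 1 | 2 | 3 |
|---|---|---|---|---|
| 150 per arm | 2 | 4 | 6 | 8 |
| 200 per arm | 1 | 3 | 5 | 7 |

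At 150 per arm, with 1 Edoxaban event, 3 Warfarin events fail (p = 0.038) and 4 pass (p = 0.021).

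**Step 4: add Warfarin events that count under 4.1 only, at the planned rates.**

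| | Base | +1 event | +2 events | Result changed |
|---|---|---|---|---|
| 150 per arm | 79.6% | 88.0% | 93.5% | 8.4% or 13.9% of trials |
| 200 per arm | 91.8% | 95.4% | 97.6% | 3.6% or 5.8% of trials |

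These figures put the extra event in every trial. If the surplus is instead a rate of 0.5 or 1 point (150 × 0.005 = 0.75 or 150 × 0.01 = 1.5 patients), the probability of declaring non-inferiority at 150 per arm rises by 5.6 or 9.8 points.

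**Step 5: false non-inferiority at 150 per arm.** Edoxaban is truly worse by the margin under 4.2.1 (5.01% against 3.51%), and test size is controlled over the full null boundary. With no surplus the probability is 2.0%.

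| Surplus counted under 4.1 only | 0.5 point | 1 point |
|---|---|---|
| Warfarin only | 3.2% | 4.9% |
| Edoxaban only | 1.2% | 0.7% |
| Equal in both arms | 2.0% | 2.0% |

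If size is controlled only over Warfarin rates up to 10%, the Warfarin-only row becomes 3.7% and 5.6%, from a base of 2.3%.

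**The case against.** The strongest reply is that the plan already settles the question. Section 4.2.3 cites 4.2.1 as the defined endpoint, and its adjudication sentence follows soon after, so the natural reading is that the blinded committee applies 4.2.1. Much of this stands. What remains is that 4.1 states an explicit counting rule, the 4.2.1 rationale partly supports it, and blinding the committee does not tell it which text to apply.

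The second reply is that few patients are affected. This also stands. Most blood-product cases count either way, because transfusion is its own criterion. The table row "Serious bleeding at any elevation of INR or Life-threatening bleeding" has Warfarin held, so a significant hematoma treated that way already counts as interruption of anticoagulation. The rows for patients without bleeding fall outside the 4.1 sentence altogether.

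The third reply is that results near the expected counts are robust. With 1 Edoxaban event, both 5 and 4 Warfarin events pass. With none, which has probability 0.995^150 = 47% at the planned rate, 2 are enough. That is correct: the sensitivity lies in borderline counts.

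A reader might go further and infer that the trial is biased toward Edoxaban. The documents do not support that. They give no count of affected patients, and 4.2.1 names anti-Xa and clinical guidance "to guide use of reversal with blood products or transfusion" for Edoxaban, so some Edoxaban cases could differ too. A reader might also obtain larger figures than those in Step 4 by removing events from counts generated at 3.51%. That treats 3.51% as the rate under the 4.1 rule, which the documents do not say.

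**Conclusion.** The contradiction is real and should be fixed; its effect is a sensitivity, not a demonstrated bias. Followed as written, 4.1 gives a different primary count from 4.2.1 for a narrow group whose size is not in the documents.

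At 300 patients, one or two extra Warfarin events would change the non-inferiority result in about 8% or 14% of trials; at 400 patients, in about 4% or 6%. False non-inferiority exceeds 2.5% only if the surplus falls on Warfarin alone or mainly there. That direction is plausible, given open-label treatment and vitamin K guidance confined to one drug class, but it is not established. These figures rest on the assumed exact test, on 3.51% being the Warfarin rate under 4.2.1, and on an assumed number of affected patients. The finding that the two passages conflict needs none of these assumptions.

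**What to change.** Before any event is adjudicated and before the 200-patient interim analysis, reconcile the two passages so that one definition governs counting in both arms. Section 4.2.3 already cites 4.2.1, so the simplest change is:

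1. Replace the counting sentence in Section 4.1 with: *Such a patient is counted as having met the primary endpoint only if a criterion in Section 4.2.1 is met.*
2. Name Section 4.2.1 in the adjudication charter as the study definition for both arms.
3. Tabulate by arm the patients who meet the 4.1 wording but no 4.2.1 criterion, so that the size of the difference can be seen.

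This changes counting and reporting, not patient care. It costs one protocol sentence, one charter line and one table. The possible downside is power: if 3.51% was meant to include events that count under 4.1 only, fewer Warfarin events will be counted. With a counted Warfarin rate of 3.0%, exact power at 300 patients is about 72%, against 79.6% as planned.

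### Sections 4.1 and 4.2.1 disagree on whether a procedural bleed given vitamin K or blood products, without a severity criterion, is a primary event

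*Combined protocol and SAP*

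**What the plan says.** Section 4.1 (Overview) deals with acute bleeding at the procedure: "blood products or vitamin K may be administered. In this case, the patient will be counted as having met the primary endpoint". It sets no severity level and does not refer to another section.

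Section 4.2.1 (Primary Endpoint) lists the events that define major bleeding. Its reversal item is conditional: "Use of reversal agent injection to control bleeding leading to clinically manifest shock", or to death, severe symptomatic hypotension, angina or hemoglobin below 8 gm%, where conservative measures do not suffice. A separate item is "Significant hematoma requiring further surgery, resulting in prolongation of hospitalization, or requiring interruption of oral anticoagulation therapy". Another is blood transfusion. The rationale that opens 4.2.1 mentions no severity level: "the need for intervention with vitamin K or blood products is recognizable to patients".

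The vitamin K table in 4.2.1 is for patients on vitamin K antagonists. For serious bleeding it says to hold Warfarin and "Administer intravenous vitamin K 5 mg to 10 mg by slow infusion or administer blood products as appropriate". Its footnote also allows vitamin K or blood products without major bleeding when the INR is mildly to moderately raised. For Edoxaban, 4.2.1 names only blood products or transfusion for reversal.

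Section 4.2.3 acknowledges the bias risk of an open-label design. It answers that "we have defined a primary endpoint with minimal patientivity (see section 4.2.1") and that there will be a "blinded adjudication committee review each potential primary endpoint event to confirm that the study definition has been met". Section 7 gives a hospital order for vitamin K or blood products as an example of documentation of intervention.

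**The concern.** One bleed can be a primary event under 4.1 and not under 4.2.1, and no sentence says which section decides. Giving vitamin K is a clinician's choice made with knowledge of the arm, and the protocol describes it only for Warfarin-type drugs. If sites or analysts follow 4.1 as written, extra events could be added mainly to Warfarin. That would help Edoxaban in the non-inferiority test and in the superiority test that may follow. With so few events expected, a single classification can matter.

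**Working it through.** **1. Where the two rules differ.**

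| Procedural bleed | 4.1 | 4.2.1 |
|---|---|---|
| Transfused | counts | counts |
| Significant hematoma needing surgery, a longer stay or anticoagulant interruption | counts if given vitamin K or blood products | counts |
| Vitamin K given, with shock, angina, hemoglobin below 8 gm% or another listed consequence | counts | counts |
| Vitamin K only, no 4.2.1 item met | counts | does not count |
| Non-transfusion blood product only, no 4.2.1 item met | counts | not clearly counted |

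Only the last two rows are in dispute. Vitamin K for a raised INR without a bleed scores under neither rule. Section 4.1 also requires that "Eligible subjects must be stable on a therapeutic dose of Warfarin (INR 2-3) for three weeks prior to randomization", which limits raised INRs, although the procedure follows 5 to 15 days later.

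**2. The plan's own figure.** Inputs from Section 10.2: Warfarin 3.51%, Edoxaban 0.5%, margin 1.5%, 300 patients (150 per arm at 1:1). One-sided alpha is 0.025 (Section 10).

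- SE = √[(0.0351 × 0.9649 + 0.005 × 0.995)/150] = 0.01609
- Power = Φ[(0.0351 − 0.005 + 0.015)/0.01609 − 1.96] = Φ(0.84) = 80.0%

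This reproduces the stated figure of about 80%. An exact score test gives 79.6%.

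**3. What one patient can do.** Section 10.3 says only that an exact test is used. I assume the exact unconditional test based on the Farrington-Manning score statistic. Expected Warfarin events are 150 × 0.0351 = 5.3, or 200 × 0.0351 = 7.0.

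| Edoxaban events | Warfarin events needed, 150 per arm | Warfarin events needed, 200 per arm |
|---|---|---|
| 0 | 2 | 1 |
| 1 | 4 | 3 |
| 2 | 6 | 5 |
| 3 | 8 | 7 |

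At 150 per arm with 1 Edoxaban event, 3 Warfarin events fail and 4 succeed.

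**4. Illustrative error rates.** These apply only if 4.1 is used to count events while 4.2.1 is the intended endpoint. Edoxaban is set worse by the full margin on the 4.2.1 endpoint: 3.51% + 1.5% = 5.01%. Extra events are added to Warfarin only. At 150 per arm the ranges reflect how widely the nuisance Warfarin rate is searched (full range, or up to 30%).

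| Assumed addition to Warfarin | False non-inferiority, 150 per arm | 200 per arm |
|---|---|---|
| None | 2.0–2.3% | 2.25% |
| +0.25 point | 2.6–3.0% | 3.0% |
| +0.5 point | 3.2–3.7% | 3.9% |
| +1.0 point | 4.9–5.6% | 6.2% |
| Exactly one patient | 3.4–3.9% | 3.6% |

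The documents give no rate for such bleeds, so every addition is an assumption. None is trivial: one patient in 150 is 0.67 point, or 0.67/3.51 = 19% of the planning rate.

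**The case against.** The strongest reply is that 4.2.1 is the only section that defines the endpoint. Section 4.2.3 cites it just before naming the blinded committee, and the synopsis has all events adjudicated. On that reading 4.1 is an overview sentence that flags a case for review, and the effect is near zero. This largely stands, and 4.2.1 is the better reading. It does not remove the conflict. Section 4.1 is worded as a rule, and both the 4.2.1 rationale and Section 7 mention vitamin K without severity, so a site that follows 4.1 is following the protocol.

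The disputed group may also be empty. Serious bleeding on Warfarin means holding the drug, and a significant hematoma that requires interruption already scores. That narrows the group, but the table footnote foresees vitamin K without major bleeding, so it cannot be ruled out.

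The direction is not certain either. Section 4.1 also counts blood products without a severity level, and 4.2.1 foresees these for Edoxaban. Some disputed events could therefore fall in either arm. That the net effect leans against Warfarin is a plausible inference which the documents do not establish.

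Finally, any misclassified event can flip a trial with about five expected. That is true. What is particular here is that the protocol's own text invites the misclassification.

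**Conclusion.** The inconsistency is real and narrow, and should be resolved before events are adjudicated. It concerns procedural bleeds treated with vitamin K or a non-transfusion blood product that meet no 4.2.1 item. Their frequency is unknown and possibly zero. If they occur and are counted, vitamin-K-only cases would plausibly favour Edoxaban, and one of them can be enough to change the conclusion.

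A reader might infer that the type I error is inflated to 3.4–3.9%. The documents do not support that. If 4.2.1 is applied throughout, nothing changes. If 4.1 is the intended endpoint, these bleeds are true events and the test keeps its nominal size. The figures describe only the mixed case, with assumed additions to one arm. A reader might also infer that any vitamin K use scores; 4.1 limits the rule to an acute procedural bleed.

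The cut-offs rest on the assumed form of exact test.

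**What to change.** Replace the 4.1 sentence with: *A procedural bleed treated with blood products, vitamin K or another reversal agent is sent for blinded adjudication and counts only if it meets a criterion in Section 4.2.1, which governs in both arms; giving a reversal agent without a 4.2.1 criterion does not score.*

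In the transfusion item of 4.2.1, state whether non-transfusion blood products such as plasma or concentrates count, with the same rule in both arms. Keep the vitamin K table as clinical guidance. In the SAP, tabulate treated but non-qualifying bleeds by arm, and repeat the primary test with them counted as a sensitivity analysis. If the sponsor does intend vitamin K treatment to be an event, that should be written into 4.2.1 with an equivalent Edoxaban criterion.

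The cost is a short amendment to two sections, one table and one analysis. The downside is that a few treated bleeds may no longer count. The 3.51% planning rate comes from clinically significant pocket hematomas (Sections 1 and 10.1, Appendix B), so power may be unaffected. If such bleeds were inside that rate, losing 0.25 or 0.5 point would lower power from 79.6% to 76.2% or 72.3% at 150 per arm, and from 91.8% to 89.8% or 87.3% at 200 per arm.
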